4.8 OLE STUDY ANALYSES

The OLE analyses will be performed separately for the OLE Stage 1 and Stage 2.

The listings will include the treatment regimen the patient received during the main stage and during the OLE.

For Stage 1, OLE begins with the first infusion of Cycle 7. As with the main study, cycles are 28 days in length. The "OLE Baseline" consists of assessments at the end of Cycle 6 / beginning of Cycle 7 (pre-dose).

For Stage 2, OLE begins with the first infusion of Cycle 10. As with the main study, cycles are 28 days in length. The "OLE Baseline" consists of assessments at the end of Cycle 9 / beginning of Cycle 10 (pre-dose).

The synopses for the OLE are in Appendix 2 and Appendix 4.

The primary and secondary endpoints for both stages, will be also produced on the OLE population when applicable. The OLE tables will be classified as per the original dose

received on the main stage and overall. For subjects who change doses, improvement will be analyzed.

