### **7.11.1 Bone Marrow Biopsy**

Bone marrow biopsy will be performed at screening, Cycle 4, Day 1, Cycle 7, Day 1, and Cycle 9, Day 29. Analysis will include confirmation of diagnosis and assessments of reticulin stain and trichrome stain. Slides will be sent to a central committee of hematopathologists who will be

blinded to subject, treatment, and collection time for centralized grading of fibrosis. A charter will be established for the central committee. Quantification of marrow fibrosis will be performed in a blinded fashion by computer assisted image analysis. Unstained slides will be collected for analysis of disease and mechanism related changes.

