**Bone Marrow Biopsies:**

An optional bone marrow biopsy will be performed every 12 weeks.

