#### Bone Marrow Biopsies:

A bone marrow biopsy will be performed only to determine or confirm a change in response category. This will be done at the following time points depending on the subjects' response category at the time of the most recent bone marrow biopsy:

- CR: Bone marrow biopsy will be done only if there is a change in status indicating potential disease progression.
- PR: For subjects with bone marrow histological remission, bone marrow biopsy (BMB) will be done only if there is a change in status indicating disease progression. For subjects without bone marrow histological remission BMB will be done every 6 months until CR is documented or until indication of potential disease progression.
- CI: BMB will be done if the clinical status changes from CI to PR or PD
- Stable disease with improvement in bone marrow fibrosis: BMB will be done if the clinical status changes from SD to CI, PR, or PD.

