4.1.4 Open Label Extension Population

For both stages, the OLE population consists of all subjects who received at least one dose of rhPTX-2 during the OLE phase.

4.1.5 Open Label Extension Subjects with Bone Marrow Biopsy Population

For both stages, the OLE patient populations with BM biopsy consist of all subjects who received at least one dose of rhPTX-2 during the OLE phase and have at least one BM biopsy result available during the OLE.

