4.4 EFFICACY ANALYSIS

All analyses will be performed separately for each stage.

4.4.1 Primary Efficacy Endpoint

Stage 1:

The ORR will be compared against a fixed level of 10% using one-proportion Z-test.

The hypothesis test will be performed separately in each of the 4 treatment groups and overall, each at the 5% significance level (one-sided; statistical significance will be concluded if the lower bound of the 2-sided 90% CI is above 10%).

Subjects with no post-baseline IWG response assessments will be considered non-responders.

Stage 2:

The BMRR will be described as the percent of subjects with a reduction in bone marrow fibrosis score by at least one grade from baseline to any time of the study.

The BMRR will be presented within each treatment group with the corresponding 95% CI.

The BMRR will be analyzed using a logistic regression with bone marrow response at any time during the study (yes/no) as response variable and treatment group as explanatory variable. The analysis will be adjusted on randomized stratum. Pairwise comparisons between the 3 treatment groups will be performed.

Two pairwise comparisons (3 mg/kg versus 0.3 mg/day and 10 mg/kg versus 0.3 mg/day) will be computed with the aim to demonstrate superiority and therefore, will use an adjusted two-sided level of significance of 0.025. The third comparison (10 mg/kg versus 3 mg/kg) is not expected to have enough power to demonstrate any difference with the planned sample size. This comparison is considered exploratory and will be conducted using an unadjusted two-sided 0.05 level of significance.

The protocol proposed a threshold of 10% as the lower limit for clinically relevant response. For the 3 mg/kg and 10 mg/kg groups, the lower limit of the 97.5% two-sided confidence interval will be compared to this threshold of 10%. If the lower limit of the confidence interval is above 10%, the corresponding dose will be claimed to have demonstrated clinically relevant efficacy.

For subjects with no readable post-baseline BM biopsy results available, the conservative rule to consider them as non-responders will be used.

4.4.2 Secondary Efficacy Endpoints

Stage 1:

For Stage 1, no formal hypothesis testing will be performed for the secondary efficacy endpoints. All summaries will be presented by treatment group and overall.

The bone marrow biopsy results will be analyzed as:

- Myelofibrosis grade shifts relative to baseline at Weeks 12 and 24.

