4.9 MISSING DATA

All available efficacy and safety data will be included in data listings and tabulations. No imputation of values for missing data will be performed. Subjects with missing post baseline response data, for any reason, will be counted as non responders.

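### Read literally, SAP 4.8 and 4.9 count extension subjects without an optional or triggered biopsy as marrow non-responders, which dilutes the Stage 2 by-visit marrow response rate

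*SAP*

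**What the plan says.** **Population.** SAP 4.8 states: "The primary and secondary endpoints for both stages, will be also produced on the OLE population when applicable". SAP 4.1.4 defines that set: "the OLE population consists of all subjects who received at least one dose of rhPTX-2 during the OLE phase". No biopsy is needed to belong to it. SAP 4.1.5 adds a narrower set, for both stages, of extension subjects who also "have at least one BM biopsy result available during the OLE". No later section assigns an analysis to that narrower set.

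**Missing response.** SAP 4.9 states: "Subjects with missing post baseline response data, for any reason, will be counted as non responders". It makes no exception for the extension. SAP 4.4.1 has a parallel rule for the Stage 2 primary endpoint: "For subjects with no readable post-baseline BM biopsy results available, the conservative rule to consider them as non-responders will be used".

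**Biopsy schedules.** In the Stage 2 main study biopsies are scheduled (Protocol 7.11.1): "Bone marrow biopsy will be performed at screening, Cycle 4, Day 1, Cycle 7, Day 1, and Cycle 9, Day 29". In the Stage 2 extension (Protocol Appendix J): "An optional bone marrow biopsy will be performed every 12 weeks". In the Stage 1 extension (Protocol Appendix L): "A bone marrow biopsy will be performed only to determine or confirm a change in response category". The exception is partial remission without histological remission in the marrow, where a biopsy is due every six months.

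**Endpoints.** The Stage 2 secondary endpoints in SAP 2.2.2 include the marrow response rate at each visit. SAP 4.8 classifies extension tables by original main-stage dose and overall. It defines an OLE Baseline at the end of the main stage but ties it to no endpoint.

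**The concern.** The non-responder rule is conservative when biopsies are scheduled for everyone, because a missing result is then an exception. In the extension a missing biopsy is an expected outcome of the design. A Stage 2 subject may decline it. A Stage 1 subject with stable disease and marrow improvement has none unless the response category changes. Applying the main-stage rule to such visits records as failure something that was never observed and often never due.

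Appendix J gives the Stage 2 extension two efficacy aims: duration of response beyond 36 weeks, and the effect of changing dose in subjects without a response. A by-visit rate that falls as uptake falls serves neither. Because the tables are split by original dose, a difference in willingness to be biopsied could be read as a difference between doses.

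The baseline is a second gap. A subject who improved by one grade by week 36 and stays there is a responder against the pre-Cycle 1 biopsy, but shows no reduction against the OLE Baseline. The SAP does not say which applies to marrow response.

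**Working it through.** The documents state no extension response rate and no biopsy uptake, and SAP 2.5 sets no extension sample size. There is therefore no planned figure to reproduce, and the numbers below are illustrative.

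**Inputs**
- Response among biopsied subjects, p = 46%: the planning rate for 10 mg/kg (Protocol 10.1).
- Share already responding on main-stage biopsies, q = 46% or 5%: the planning rates for 10 mg/kg and 0.3 mg/kg (Protocol 10.1).
- Uptake of extension biopsies, u: assumed.
- New response among main-stage non-responders if biopsied, r = 20%: assumed.

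**1. Stage 2 response rate at an extension visit, all dosed subjects, missing counted as non-response.** A main-stage biopsy cannot supply the result for an extension visit, so the reported rate = u × p.
- u = 80%: 0.80 × 0.46 = 36.8%
- u = 50%: 0.50 × 0.46 = 23.0%
- u = 30%: 0.30 × 0.46 = 13.8%

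**2. Two original dose groups with the same true 46% but different uptake.**
- u = 30%: 13.8%
- u = 60%: 0.60 × 0.46 = 27.6%

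Uptake alone produces a gap of 27.6 − 13.8 = 13.8 percentage points.

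**3. The same visit on the SAP 4.1.5 population.** The rate is 46% at any uptake, provided the biopsied subjects are representative. That is not assured.

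**4. Primary Stage 2 response, original baseline, any point in the study.** Main-stage biopsies count, so the rate = q + (1 − q) × u × r.
- q = 46%: 46.0% at u = 0, and 0.46 + 0.54 × 0.20 = 56.8% at u = 100%.
- q = 5%: 5% at u = 0, and 0.05 + 0.95 × 0.20 = 24% at u = 100%.

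Uptake moves this endpoint modestly where main-stage response is high and more where it is low. On the planning assumptions, low response is expected at 0.3 mg/kg, whose subjects change dose on entering the extension.

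**5. Endpoints that a missing extension biopsy does not turn into failure.**
- Stage 1 overall response can be met by clinical improvement through anemia, spleen or symptoms (Protocol Appendix B). The route through stable disease plus marrow improvement does need a biopsy (SAP 2.2.1).
- Duration of marrow response is defined among responders and censored at the last marrow assessment (SAP 2.2.2 and 4.4.2). A missing biopsy brings censoring forward and does not count as loss of response.
- The Stage 1 secondary marrow endpoint is a grade shift, not a responder rate.

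**The case against.** The strongest reply is that the text leaves room for the sensible analysis. SAP 4.8 says the endpoints are produced where applicable, and SAP 4.1.5 exists, evidently for marrow results, so the omission may be a missing cross-reference. The Protocol also lists the by-visit rate only at weeks 12, 24 and 36, so it might not be meant for extension visits. This is fair as to intent. It does not settle what is written: SAP 4.8 names the other population, SAP 2.2.2 gives the rate at each visit, the applicability qualifier is undefined, and SAP 4.9 has no exception. Two programmers could reasonably produce different denominators.

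A reader might infer that every extension marrow result mainly measures biopsy uptake. The documents do not support that. Stage 2 subjects enter after nine cycles with three scheduled post-baseline biopsies behind them, so for the primary response they would ordinarily not be missing post-baseline data at all. Nor are Stage 1 responders through clinical improvement, or marrow durations, scored as failures.

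A reader might also infer that SAP 4.8 resets the baseline for marrow response, or tests the extension rate against 10%. It does neither: it defines an OLE Baseline without tying it to marrow response, and it states no such comparison.

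Finally, restricting to biopsied subjects exchanges dilution for self-selection. That stands, and is why both counts should be shown.

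**Conclusion.** The concern holds for the Stage 2 by-visit marrow response rate at extension visits. Under the literal rules a 46% rate among biopsied subjects would be reported as 37%, 23% or 14% at 80%, 50% or 30% uptake, and unequal uptake between original dose groups could mimic a dose effect. These figures rest on assumed uptakes, on a main-stage planning rate carried into the extension, and on biopsied subjects being representative.

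The effect on the primary Stage 2 response is smaller and matters mainly where main-stage response is low. The unused 4.1.5 population and the unspecified baseline are confirmed from the text. The point should be settled in this SAP, because it was written to govern the final analysis including both extensions.

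**What to change.** In SAP 4.8 and 4.9:
- Report extension marrow response by visit, and marrow grade shifts, on the 4.1.5 population. Show the number biopsied over the number dosed, by original dose. The all-dosed rate may be shown alongside.
- State that counting missing response as non-response does not apply to optional or untriggered extension biopsies.
- Use the original pre-Cycle 1 baseline for marrow response and its duration. Keep the OLE Baseline for change after a dose switch.

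The cost is SAP wording, with no new data collection. The downside is that biopsied subjects select themselves or are selected by clinical change, so the extension marrow results remain descriptive.

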4.9 MISSING DATA

All available efficacy and safety data will be included in data listings and tabulations. No imputation of values for missing data will be performed. Subjects with missing post baseline response data, for any reason, will be counted as non responders.


APPENDIX K: SYNOPSIS: STAGE I

Sponsor:

Promedior, Inc

Name of Finished Product:

Recombinant human Pentraxin-2: PRM-151

Study Title:

A Phase 2, Open-Label, Prospective Study Of PRM-151 In Subjects With Primary Myelofibrosis (PMF), Post-Polycythemia Vera MF (post-PV MF), Or Post-Essential Thrombocythemia MF (post-ET MF)

Study Number:

PRM-151G-101

Study Phase: Phase 2

Investigational Product; Dose; and Mode of Administration:

PRM-151 10 mg/kg intravenous

Comparator; Dose; and Mode of Administration:

Not applicable

Primary Objective(s):

• To evaluate the efficacy of two different dose schedules of PRM-151 in intermediate-1, intermediate-2, or high risk subjects with PMF, post-PV MF, or post ET-MF who are not receiving therapy for MF, and in subjects with PMF, post-PV MF, or post ET-MF on a stable dose of ruxolitinib for at least three months.

Secondary Objective(s):

- To evaluate the safety and tolerability of two different dose schedules of PRM-151 in intermediate-1, intermediate-2, or high risk subjects with PMF, post-PV MF, or post ET-MF who are not receiving therapy other than transfusions, and the safety and tolerability of two different dose schedules of PRM-151 in subjects with PMF, post-PV MF, or post ET-MF on a stable dose of ruxolitinib
- To assess the effect of PRM-151 on bone marrow fibrosis
- To measure the duration of response
- PK of PRM-151 in subjects receiving single agent PRM-151 and in subjects receiving ruxolitinib.

Exploratory Objectives

- To evaluate the effect of PRM-151 on plasma cytokine levels comparing baseline on Cycle 1, Day 1 to Day 1 of Cycles 2, 3, 4 and Day 29 of Cycle 6
- To evaluate the effect of PRM-151 on PBMC mRNA and miRNA expression levels comparing baseline on Cycle 1, Day 1 to Day 1 of Cycles 2, 3, 4 and Day 29 of Cycle 6
- To evaluate the correlation of baseline PTX-2 levels with outcomes.

Study Endpoints:

Primary:

- The overall response rate (ORR), defined as a clinical improvement (CI), partial remission (PR), and complete remission (CR) according to the International Working Group (IWG) Criteria (Appendix B)
- Stable disease with improvement in bone marrow fibrosis score by at least one grade according to the European Consensus on Grading of Bone Marrow Fibrosis (Appendix D) will also be considered a response (bone marrow response).

Secondary:

- Incidence of adverse events (AEs), serious adverse events (SAEs), and changes in laboratory test results
- Change in bone marrow fibrosis
- Change in the modified Myeloproliferative Neoplasms Symptom Assessment Form (MPN-SAF) Score (Appendix G)
- Duration of response
- PK parameters including C_{max} (maximum drug concentration), t_{max} (time to maximum concentration, AUC, clearance, and volume of distribution.

Exploratory:

- Changes in levels of circulating plasma cytokine levels including but not limited to CRP, IL-1ra, MIP-1β, TNFα, IL-6 and VEGF comparing baseline on Cycle 1, Day 1 to Day 1 of Cycles 2, 3, 4 and Day 29 of Cycle 6
- Changes in levels of PBMC mRNA and miRNA expression levels comparing baseline on Cycle 1, Day 1 to Day 1 of Cycles 2, 3, 4 and Day 29 of Cycle 6.
- Correlation of baseline PTX-2 levels with outcomes.

Study Design:

This is an open-label, Simon two stage, Phase 2 study to determine the efficacy and safety of two different dose schedules of PRM-151 in subjects with PMF and post ET/PV MF. There are two treatment cohorts, each assigned to one of two dose schedules of PRM-151. Subjects will be assigned to a weekly or every four week dosing schedule by the investigator based on their ability to visit the study site on a weekly basis. This is an adaptive design as defined in FDA Draft Guidance for Industry: Adaptive Design Clinical Trials for Drugs and Biologics, February 2010. Modifications to dose levels, schedule, or regimen may be made in Stage 2 based on data from Stage 1.

Stage 1:

Cohort 1: Approximately 12 subjects with intermediate-1, intermediate-2, or high risk MF who have received no treatment for MF in at least two weeks will be enrolled and assigned to treatment with single agent PRM-151 at a dose of 10 mg/kg IV on Days 1, 3, 5, 8, 15, and 22 of Cycle 1 and Days 1, 8, 15 and 22 of each subsequent 28 day cycle for six cycles, OR single agent PRM-151 at a dose of 10 mg/kg administered IV on Days 1, 3, and 5 of Cycle 1 and Day

1 of each subsequent 28 day cycle for six cycles Subjects responding to therapy may continue receiving it as long as there is a benefit.

Cohort 2: Approximately 12 subjects with intermediate-1, intermediate-2, or high risk MF on a stable dose of ruxolitinib for at least 12 weeks, with no improvement in spleen during the last four weeks will be enrolled. Subjects will be assigned to receive PRM-151 in combination with ruxolitinib either at a dose of 10 mg/kg administered IV on Days 1, 3, 5, 8, 15, and 22 of Cycle 1 and Days 1, 8, 15 and 22 of each subsequent 28 day cycle for six cycles, OR in combination with ruxolitinib at a dose of 10 mg/kg administered IV on Days 1, 3, and 5 of Cycle 1 and Day 1 of each subsequent 28 day cycle for six cycles. Subjects responding to therapy may continue receiving it as long as there is a benefit.

Stage 2:

If at least one response is seen in any arm of either cohort in Stage 1, an additional 20 subjects may be enrolled and treated on that dosing schedule. All non-responding arms will be closed. Subjects responding to therapy may continue receiving it as long as there is a benefit.

Enrolled subjects will be considered evaluable for response if they are on study drug for at least four weeks.

Study Duration:

Each subject will participate in the study for approximately 32 weeks. Participation will include a screening evaluation within four weeks before the first PRM-151 administration, six study cycles of four weeks each, and an end of study visit four weeks after the end of the last cycle. Subjects may continue with PRM-151 dosing in the absence of disease progression or toxicity warranting discontinuation of therapy, as long as there is evidence of clinical benefit, as judged by the Investigator.

Subjects who have no benefit in the parent study may switch to a schedule in which responses occur after completing 6 cycles of the originally assigned treatment.

It is estimated that the study will be completed in approximately 18 months.

Study Inclusion and Exclusion Criteria:

Inclusion Criteria:

- 1. Subjects must be ≥18 years of age at the time of signing the Informed Consent Form (ICF);
- 2. Subjects must voluntarily sign an ICF;
- 3. Subjects must have a pathologically confirmed diagnosis of PMF as per the WHO diagnostic criteria (see Appendix C) or post ET/PV MF (note that all diagnoses must include the presence of at least Grade 2 marrow fibrosis according to the European Consensus on Grading of Bone Marrow Fibrosis (Appendix D) with intermediate -1, intermediate -2, or high risk disease according to the IWG-MRT Dynamic International Prognostic Scoring System (see Appendix E);
- 4. A biopsy must be performed within four weeks prior to Cycle 1 Day 1 treatment to establish the baseline fibrosis score;

- 5. Subjects must have an Eastern Cooperative Oncology Group (ECOG) Performance Status of 0-2. (Appendix F);
- 6. Life expectancy of at least six months;
- 7. At least two weeks must have elapsed between the last dose of any MF-directed drug treatments for myelofibrosis (including investigational therapies) and study enrollment, except for ruxolitinib for Cohort 2 (see Inclusion Criteria);
- 8. Recovery to ≤ Grade 1 or baseline of any toxicities due to prior systemic treatments, excluding alopecia;
- 9. Women of child bearing potential (WCBP), defined as a sexually mature woman not surgically sterilized or not post-menopausal for at least 24 consecutive months if ≤55 years or 12 months if >55 years, must have a negative serum pregnancy test within four weeks prior to the first dose of study drug and must agree to use adequate methods of birth control throughout the study. Adequate methods of contraception include use of oral contraceptives or Depo-Provera, with an additional barrier method (diaphragm with spermicidal gel or condoms with spermicide), double-barrier methods (diaphragm with spermicidal gel and condoms with spermicide), partner vasectomy, and total abstinence.
- 10. Ability to adhere to the study visit schedule and all protocol requirements;
- 11. For Cohort 2 (PRM-151 added to ruxolitinib) Subjects only:
- 12. Must have been on a stable dose of ruxolitinib treatment for at least 12 weeks with no further improvement in splenomegaly for at least four weeks;
- 13. Must have adequate organ function as demonstrated by the following:
 - ALT (SGPT) and/or AST (SGOT) ≤ 3x upper limit of normal (ULN), or ≤ 4 x ULN (if upon judgment of the treating physician, it is believed to be due to extramedullary hematopoiesis [EMH] related to MF);
 - Direct bilirubin ≤ 1.5 x ULN; or ≤ 2 x ULN (if upon judgment of the treating physician, it is believed to be due to EMH related to MF);
 - Serum creatinine $\leq 2.5 \text{ mg/dL x ULN}$.

Exclusion Criteria:

- 1. Other invasive malignancies within the last 3 years, except non-melanoma skin cancer and localized cured prostate and cervical cancer;
- 2. History of stroke, unstable angina, myocardial infarction, or ventricular arrhythmia requiring medication or mechanical control within the last 6 months;
- 3. Presence of active serious infection;
- 4. Any serious, unstable medical or psychiatric condition that would prevent, (as judged by the Investigator) the subject from signing the informed consent form or any condition, including the presence of laboratory abnormalities, which places the subject at unacceptable risk if he/she were to participate in the study or confounds the ability to interpret data from the study;

- 5. Known history of human immunodeficiency virus (HIV), or known active hepatitis A, B, or C infection;
- 6. Organ transplant recipients other than bone marrow transplant;
- 7. Women who are pregnant or lactating.

Efficacy Assessments:

Efficacy will be assessed by evaluation of the overall response rate (ORR) categorized according to the International Working Group (IWG) Criteria (Appendix B) modified to include stable disease with improvement in bone marrow fibrosis by at least one grade.

Safety Assessments:

Safety will be evaluated from reported adverse events, scheduled physical examinations, vital signs, and clinical laboratory test results.

This Phase 2 clinical trial will have an independent Data Monitoring Committee (DMC) to conduct interim reviews of safety data, and provide an independent evaluation on a predetermined and ad-hoc basis of accumulating safety data. All adverse events reported to Promedior will be considered by Promedior and the DMC regardless of the reported causality by the study site. In assessing adverse events, Promedior and the DMC will consider only treatment emergent adverse events, defined as adverse events that occur after at least one exposure to study drug. The DMC will review all safety data at the following pre-determined times:

- when the first 12 subjects reach Cycle 4, Day 1
- when the first 24 subjects have completed the study

The DMC will review the following events immediately on an ad-hoc basis and will make a recommendation about whether the study may proceed:

- any death
- any event of anaphylaxis
- any SAEs
- any treatment emergent Grade 3 non-hematologic toxicity
- any treatment emergent grade 4 hematological adverse event or a treatment emergent grade 3 hematologic adverse event that represents a change of 2 grades from grade 1, or a doubling of transfusion frequency

Statistical Methods:

[figure not shown]
The objective is to demonstrate superiority within each cohort and dose schedule, comparing observed ORR in each arm to a fixed uninteresting level ORR of 0.1. Let π denote population expected value of the primary parameter ORR. The objective of the trial is to reject the null-hypothesis

$$H_0: \pi \le 0.1$$

in favor of the alternative hypothesis

$$: \pi > 0.4$$

The design will be two-staged within each arm based on Simon (Simon 1989) as shown in the figure below:

The design maintains the type I error probability at 3.4% which is less than 5%. Furthermore, for π >0.4, there is a high probability of at least 94% to demonstrate superiority. The probability under H_0 to stop after stage 1 is 53%, with implicit consequence that the expected number of subjects is 15, compared to a maximum number of subjects of 26.

Date of Original Protocol: Version 1.0 17 Jan 2013

Appendix 2 OLE Synopsis – Stage 1

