## 5. STAGE 2 SELECTION OF STUDY POPULATION

### 5.1 Study Population

#### 5.1.1. Inclusion Criteria

This Phase 2 study will enroll up to 111 subjects with MF, 27 in Stage 1, and up to an additional 84 subjects in Stage 2

Each subject must meet all of the following inclusion criteria to be enrolled in the study:

1. Subjects must be  $\geq 18$  years of age at the time of signing the Informed Consent Form (ICF);
2. Subjects must voluntarily sign an ICF;
3. Subjects must have a pathologically confirmed diagnosis of PMF as per the WHO diagnostic criteria (see [APPENDIX C](#)) or post ET/PV MF;
4. At least Grade 2 marrow fibrosis according to the WHO Grading of Bone Marrow Fibrosis ([APPENDIX D](#));
5. Intermediate -1, intermediate -2, or high risk disease according to the IWG-MRT Dynamic International Prognostic Scoring System (see [APPENDIX E](#));
6. A bone marrow biopsy must be performed within four weeks prior to Cycle 1 Day 1 treatment to establish the baseline fibrosis score;
7. Subjects must not be candidates for ruxolitinib based on EITHER:
  - a. Platelet count  $< 50 \times 10^9/L$ , OR
  - b. Hgb  $< 100$  g/L have received  $\geq 2$  units PRBC in the 12 weeks prior to study entry, and be intolerant of or had inadequate response to ruxolitinib;
8. Subjects must have an Eastern Cooperative Oncology Group (ECOG) Performance Status of 0-2. ([APPENDIX F](#));
9. Life expectancy of at least twelve months;
10. At least four weeks must have elapsed between the last dose of any MF-directed drug treatments for myelofibrosis (including investigational therapies) and study enrollment;
11. Recovery to  $\leq$  Grade 1 or baseline of any toxicities due to prior systemic treatments, excluding alopecia;

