**$H_0: \pi < 0.1$**

in favor of the alternative hypothesis

$$H_A: \pi > 0.4$$

The design will be two-staged within each arm based on Simon (Simon 1989) as shown in the figure below:

The design maintains the type I error probability at 3.4 % which is less than 5 %. Furthermore, for  $\pi > 0.4$ , there is a high probability of at least 94 % to demonstrate superiority. The probability under  $H_0$  to stop after stage 1 is 53 %, which implicit consequence that the expected number of subjects is 15, compared to a maximum number of subjects of 26.

**Date of Original Protocol:** Version 1.0 17 Jan 2013

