2.5 DETERMINATION OF SAMPLE SIZE

Details regarding the sample size for Stage 1 and Stage 2 are described in the Appendix 1 and Appendix 3 (Protocol Synopsis).

For the OLE, no target sample size was delineated. The sample size was determined by the number of subjects who rollover from the main study. The study was intended to provide access to rhPTX-2 for any subjects in the main study for whom the investigator felt clinical benefit could be realized or extended.

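### The 94% power and 3.4% type I error that SAP 2.5 cites for Stage 1 belong to a Simon two-stage design whose second step was not run, not to the single-look arm tests in SAP 4.4.1

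*SAP*

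**What the plan says.** SAP 2.5 contains no Stage 1 sample-size reasoning of its own: "Details regarding the sample size for Stage 1 and Stage 2 are described in the Appendix 1 and Appendix 3". Appendix 1 reproduces the Stage 1 protocol synopsis (Protocol Appendix K). Its objective is superiority within each cohort and dose schedule, "comparing observed ORR in each arm to a fixed uninteresting level ORR of 0.1". On the design it says: "The design will be two-staged within each arm based on Simon". It then gives a type I error of 3.4%, a 53% chance of stopping after the first step under the null, an expected number of 15, a maximum of 26, and, for an ORR above 0.4, "there is a high probability of at least 94% to demonstrate superiority". The second step is described earlier in the same synopsis: after at least one response in an arm, "an additional 20 subjects may be enrolled and treated on that dosing schedule".

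Protocol 5.1.1 gives the enrolment as "27 in Stage 1, and up to an additional 84 subjects in Stage 2". Protocol 1.5 records that every Stage 1 arm met the one-response criterion. It then describes Stage 2 as a randomised, blinded comparison of three single-agent doses with narrower eligibility and a different primary endpoint.

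For the Stage 1 primary analysis, SAP 4.4.1 specifies a one-proportion Z-test of ORR against 10%: "The hypothesis test will be performed separately in each of the 4 treatment groups and overall, each at the 5% significance level". The test is one-sided, and significance is read from the lower bound of a two-sided 90% interval. No two-stage rule and no power are given there.

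**The concern.** The only operating characteristics the SAP offers for Stage 1 rest on up to 26 subjects per arm and a two-step rejection rule. The test it specifies has one look and, on any roughly even split of 27 subjects over four arms, 6 or 7 subjects per arm. If the power of that test is much lower, a reader who follows SAP 2.5 will credit each arm-level result with sensitivity it does not have. A non-significant arm could then be taken as good evidence that the schedule or the ruxolitinib combination falls short of 40%. The stated type I error has the same problem: 3.4% is not the error rate of the 4.4.1 rule.

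**Working it through.** **Inputs.** Null ORR 0.10, alternative 0.40, 20 added subjects and maximum 26 (SAP Appendix 1). Stage 1 total of 27 (Protocol 5.1.1), or two cohorts of about 12 over two schedules each (SAP Appendix 1). Rule: lower bound of the two-sided 90% interval above 10% (SAP 4.4.1). Arm sizes are not documented, so 24/4 = 6 and 27/4 = 6.75 are assumptions of an even split.

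**Step 1: reproduce the stated figures.** Take n1 = 6, stop at 0 responses, add 20, reject at 6 or more of 26.

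- Early stop under the null: 0.9^6 = 0.531 (stated 53%)
- Expected number: 6 + (1 − 0.531) × 20 = 15.4 (stated 15)
- P(reject | 0.10) = 0.0339 (stated 3.4%)
- P(reject | 0.40) = 0.938 (stated at least 94%, so correct to rounding)

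The plan's figures are therefore those of a 6 + 20 Simon design in each arm, and they depend on the second step.

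**Step 2: was the second step run?** Protocol 1.5 replaces the expansions with the randomised three-dose trial. One of its arms again uses 10 mg/kg every four weeks, but eligibility and primary endpoint differ. SAP 4.4 analyses each stage separately, so those subjects do not enter the Stage 1 test.

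**Step 3: the 4.4.1 rule.** With c the smallest number of responders that counts as significant, power is P(X ≥ c | n, 0.40) and actual type I error is P(X ≥ c | n, 0.10). The SAP does not name the interval method, so c can depend on it. For 2 of 6:

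- Z with null standard error: (0.333 − 0.10)/√(0.09/6) = 1.91 > 1.645, so significant (equivalent to the Wilson bound)
- Wald lower bound: 0.333 − 1.645 × √(0.333 × 0.667/6) = 0.017 < 0.10, so not significant
- Exact: P(X ≥ 2 | 6, 0.10) = 0.114 > 0.05, so not significant

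Hence at n = 6:

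- c = 2: power = 1 − 0.6^6 − 6(0.4)(0.6^5) = 1 − 0.0467 − 0.1866 = 0.767
- c = 3: subtract a further 15(0.4²)(0.6⁴) = 0.3110, giving 0.456

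At n = 7, all three bounds need 3 responders: 1 − 0.0280 − 0.1306 − 0.2613 = 0.580.

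| Group | n | c | Bound | Power at 0.40 | Actual type I error |
|---|---|---|---|---|---|
| One arm | 6 | 2 | Score/Wilson | 0.767 | 0.114 |
| One arm | 6 | 3 | Wald, exact | 0.456 | 0.016 |
| One arm | 7 | 3 | All three | 0.580 | 0.026 |
| Overall | 24 | 5 | Score/Wilson | 0.987 | 0.085 |
| Overall | 24 | 6 | Wald, exact | 0.960 | 0.028 |
| Overall | 27 | 6 | Score/Wilson, exact | 0.985 | 0.047 |
| Overall | 27 | 7 | Wald | 0.958 | 0.015 |

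**Step 4: sensitivity to uneven arms.** Stage 1 allocation was by investigator choice, so arms may be unequal. Power across the three bounds is 0.32–0.66 at n = 5, 0.41–0.68 at n = 8, 0.62–0.83 at n = 10 and 0.77–0.92 at n = 12. The upper ends at n = 10 and n = 12 are Wilson results with actual type I errors of 7.0% and 11.1%. One arm of 12 would leave 15 of the 27 for the other three, an average of 5.

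**The case against.** The strongest defence is that Appendix 1 is a reproduced synopsis of how Stage 1 was planned. Its expansion is optional in wording, it allows dose, schedule or regimen to be modified, and Protocol 1.5 tabulates the redesign openly. SAP 4.4.1 sets its own 5% level and cites neither 94% nor 3.4%. This stands as an account of how the mismatch arose. It does not remove it: SAP 2.5 makes the synopsis the current sample-size basis, and no passage withdraws its figures.

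It can also be said that power is moot for a stage already analysed, since this SAP was signed before the final extension database lock. Power at the design alternative of 40% and the treated arm size is still a property of the rule. It is not power computed from the observed rate, so it remains a fair replacement for the figure now cited.

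Four stronger readings are tempting and are not supported:

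- A reader might infer that the 94% is an arithmetic error. It is correct for its own design, and 26 is the maximum per arm, not a fixed size.
- A reader might infer a guaranteed minimum shortfall, such as 94 − 77 = 17 points. Arm sizes are unknown, and the Wilson results at n = 10 and n = 12 lie closer to 94%.
- A reader might infer that the report will present the arm tests as having 94% power, or non-significant arms as failures. The documents do not say so. SAP 2.6 even calls the study non-inferential, which sits awkwardly with five Stage 1 significance tests.
- A reader might infer that the overall test should become the only Stage 1 hypothesis test. That conflicts with the stated per-arm objective and pools single-agent with ruxolitinib-combination subjects. It would also select the best-powered test after results are known. Whether the arm tests were pre-specified in the earlier Stage 1 SAP cannot be checked from these documents.

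**Conclusion.** The concern holds for the sample-size basis. The 94% and 3.4% are correct for a 6 + 20 Simon design per arm but are not properties of the single-look arm tests in SAP 4.4.1. Assuming an even split, power at 40% ORR is 46% or 77% at n = 6 and 58% at n = 7, so a true 40% rate would be missed in about 23% to 54% of cases. The 77% is reached only with a bound whose actual type I error (11.4%) exceeds the SAP's 5%; bounds that hold 5% give 46% to 58% at these sizes. The overall test, at 96–99% with 24 to 27 subjects, is the only one near the stated power. The exact shortfall rests on undocumented arm sizes and an unnamed interval method. The mismatch between the cited design and the specified test does not.

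**What to change.** In SAP 2.5, state that the 20-subject Simon step was not enrolled in any Stage 1 arm, and that the 3.4%, 94% and maximum of 26 in Appendix 1 do not apply to the tests in 4.4.1. Replace them with the power at 40% ORR and the actual type I error of the 4.4.1 rule, at the arm sizes treated and overall, naming the interval method used. Keep the arm-level tests, because the stated objective is superiority within each cohort and schedule. Add to 4.4.1 that a non-significant arm is not evidence that its ORR is below 40%.

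The change is to SAP text only and needs no new subjects or data. Its cost is that the stated arm-level power becomes much less favourable.
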